# 4.5. Elimination criteria during the study

The following criteria should be checked at each visit subsequent to the first visit. If any become applicable during the study, it will not require withdrawal of the subject from the study but may determine a subject's evaluability in the according-to-protocol (ATP) analysis. See Section 10.4 for definition of study cohorts to be evaluated.

- Use of any investigational or non-registered drug or vaccine other than the study vaccine(s) during the study period.
- Chronic administration (defined as more than 14 days) of immunosuppressants or other immune-modifying drugs during the study period (for corticosteroids, this will mean prednisone, or equivalent, ≥ 0.5 mg/kg/day. Inhaled and topical steroids are allowed).
- Administration of a vaccine not foreseen by the study protocol during the period starting from 30 days before each dose of vaccine(s) and ending 30 days after.
- Administration of immunoglobulins and/or any blood products during the study period.
- Administration of either TETRActHib or study vaccines in the incorrect limb.

• Failure to thrive

(Amended 12 April 2005).

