# 4.4. Exclusion criteria for enrollment

The following criteria should be checked at the time of study entry. If any apply, the subject must not be included in the study:

- BCG administration within one week of proposed administration of a study vaccine.
- Use of any investigational or non-registered drug or vaccine other than the study vaccines within 30 days preceding the first dose of study vaccine, or planned use during the study period.
- Administration of immunoglobulins and/or any blood products since birth or planned administration during the study period.
- Chronic administration (defined as more than 14 days) of immunosuppressants or other immune-modifying drugs since birth (for corticosteroids, this will mean prednisone, or equivalent, ≥ 0.5 mg/kg/day. Inhaled and topical steroids are allowed).

- Any chronic drug therapy to be continued during the study period.
- Previous vaccination with diphtheria, tetanus, pertussis (whole-cell or acellular), *Hemophilus influenzae* type b or hepatitis B vaccines.
- Major congenital abnormality.
- Serious acute or chronic illness determined by clinical, physical examination and laboratory screening tests
- Any medically diagnosed or suspected immunodeficient condition based on medical history and physical examination (no laboratory testing required)
- A family history of congenital or hereditary immunodeficiency.
- History of allergic disease or reactions likely to be exacerbated by any component of the vaccine.
- History of any neurological disorders or seizures.
- Maternal death.
- Moderate malnutrition at screening defined as weight for age Z-score less than -2; this corresponds to a weight of ≤ 3.9 kg for 2 month old boys and ≤ 3.6 kg for 2 month old girls (*Amended 17 January 2005*).
- Hemoglobin < 80 g/L
- Simultaneous participation in any other clinical trial.
- Same sex twin
- Any other findings that the investigator feels would increase the risk of having an adverse outcome from participation in the trial.

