## 4.6. Contraindications to any vaccination dose

The following AEs constitute contraindications to administration of RTS,S/AS02D at that point in time; if any one of these AEs occurs at the time scheduled for vaccination, the subject may be vaccinated at a later date, within the time window specified in the protocol (see Section 5.3), or withdrawn at the discretion of the investigator (see Section 9). The subject must be followed until resolution of the event, as with any AE (see Section 8.6).

- Acute disease at the scheduled time of vaccination. Acute disease is defined as the presence of any moderate or severe illness, or a mild illness with axillary temperature ≥ 37.5°C (all vaccines can be administered to persons with a minor illness such as diarrhea, mild upper respiratory infection with or without low-grade febrile illness).
- Axillary temperature  $\geq$  37.5°C.
- A lesion that would prevent intramuscular injection in the left or right antero-lateral thighs

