## 4.7. Contraindications to subsequent vaccination dose

The following adverse events (AEs) constitute absolute contraindications to further administration of RTS,S/AS02D. If any of these AEs occur during the study, the subject must not receive additional doses of vaccine but may continue other study procedures at the discretion of the investigator (see Section 9). The subject must be followed until resolution of the event, as with any AE (see Section 8.6):

- Anaphylactic reaction following the administration of vaccine(s).
- Any confirmed or suspected immunosuppressive or immunodeficient condition, including human immunodeficiency virus (HIV) infection.

See Section 5.1.7 for a description of how these children will receive further vaccinations with licensed vaccines.

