The process for each vaccination is as follows. The identity of the child will be confirmed using the study identification card. The subject number on this card will be cross-checked with that on the subject's clinic form, ensuring that the subject number on the clinic form matches that of the study identification card. On the day of the first vaccination the inclusion/exclusion criteria and consent form will be checked prior to vaccination. On the days of the subsequent vaccinations, elimination criteria and contraindications to vaccination will be checked prior to vaccination. A vaccine clinic form will be initiated, which will give the child's identifiers, subject number and treatment number assigned after the administration of the vaccine.

For each vaccination during the course of the study, the Vaccinator will prepare and administer the vaccine for a specific subject. Since the vaccines used in this study are of distinct appearance, the Vaccinators are not blinded and perform no other function in the study (refer to Section 6.5). The Vaccinator will select the sealed box labeled with the subject's treatment number, containing the vials numbered with the treatment number, remove the vaccine vials and fill a syringe according to this study protocol (refer to Section 6.2). The Vaccinator will then place a numbered opaque label with the subject's treatment number on the syringe. The purpose of masking the syringe is to blind the parent(s) or guardians(s) of the subject. After administering the vaccination to the subject the Vaccinator will enter the treatment number administered to the subject on the clinic form.

Subjects who cannot be vaccinated on the originally scheduled date (due to an acute illness on the judgment of the PI or designate, local lesion at the injection site or scheduling conflicts) will be vaccinated within 7 days and undergo all study procedures

for the visit on the same day as vaccination. In the particular case of any child found to be febrile (axillary temperature  $\geq 37.5^{\circ}$ C), a blood slide will be taken to investigate for malaria. Children will be treated as appropriate for their condition and will be followed up until resolution of any symptoms and be vaccinated if their clinical symptoms resolve within 7 days.

Those who cannot be re-vaccinated within 7 days of their scheduled date will continue all study procedures apart from receiving further study vaccinations.

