## **Rationale/background for changes:**

The CISM, GSK Biologicals and MVI teams have decided to remove assessment of Determinants of Vaccine Response from this study. All references to the assessment have been removed throughout the protocol.

In order to ensure that there is sufficient blood available to carry out Cell-Mediated Immunity assessment at protocol-defined timepoints it is necessary to raise the amount of blood to be collected at these timepoints from 1 mL to 2 mL. The sampling methodology is not specified per-protocol but is clarified in the informed consent documents.

A further elimination criterion has been added in order to ensure that children who fail to thrive will not receive experimental vaccine.

In order to assess the pertussis response it is necessary to account for maternally acquired immunity. Assessment of antibodies to pertussis at screening was omitted in previous versions of the protocol. This has been corrected in this amendment.

Text and a table have been added to help clarify the time periods between which different classes of oncomitant medications/treatments must be recorded.

A number of typographical errors that have been noticed since the previous amendment was finalized have been corrected in this version

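### Failure to thrive was added so that affected infants would get no further experimental vaccine, but it sits only in Section 4.5, which does not stop a dose

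*Protocol*

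**What the plan says.** Section 4.5 lists criteria to be checked at each visit after the first. If one is met, "it will not require withdrawal of the subject from the study but may determine a subject's evaluability in the according-to-protocol (ATP) analysis". Failure to thrive is the last bullet in that list, marked as added on 12 April 2005. The rationale in Appendix H for those changes states the purpose: "A further elimination criterion has been added in order to ensure that children who fail to thrive will not receive experimental vaccine".

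The rules that act on dosing are elsewhere:

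- Section 4.6 defers a dose for acute disease, for an axillary temperature of 37.5°C or more, or for a lesion at the injection site. On illness it says "Acute disease is defined as the presence of any moderate or severe illness, or a mild illness with axillary temperature" of at least 37.5°C. It adds that "all vaccines can be administered to persons with a minor illness such as diarrhea".
- Section 4.7 stops all further doses for anaphylaxis and for "Any confirmed or suspected immunosuppressive or immunodeficient condition, including human immunodeficiency virus (HIV) infection".
- Section 5.1.11 sets a time limit on deferral: "Those who cannot be re-vaccinated within 7 days of their scheduled date will continue all study procedures apart from receiving further study vaccinations". It also requires a check: "On the days of the subsequent vaccinations, elimination criteria and contraindications to vaccination will be checked prior to vaccination".
- Section 4.4 has a nutritional exclusion, but only at entry: "Moderate malnutrition at screening defined as weight for age Z-score less than -2".
- Sections 5.1.7 and 9.2.2 allow the investigator to withdraw an infant for medical reasons, or to stop the product while follow-up continues.

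**The concern.** The stated purpose concerns dosing. The section chosen to carry it concerns analysis cohorts. An investigator who applies the protocol to the letter could identify an infant as failing to thrive, tick the elimination criterion, and still give the blinded dose that the amendment was written to prevent.

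This is the first administration of RTS,S/AS02D to infants, and safety is the primary objective. What is at stake is the protection of individual infants and the same handling from one clinician to the next. If the criterion is applied, the infant may also leave the according-to-protocol cohorts (10.6.2 to 10.6.4), so the protocol may discount the data while permitting the exposure.

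**Working it through.** No figure in the protocol bears on this point, so the check is to trace an infant through each rule that could stop a blinded dose. Take an infant who met the entry criteria and is judged to be failing to thrive before one of the three blinded doses (Clinic Visits 3, 6 and 8).

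1. **Section 4.4.** The weight-for-age cut applies at screening. It does not act on an infant who falters later.
2. **Section 4.6.** If the infant is also moderately or severely ill, febrile, or has a thigh lesion, that day's dose is deferred. If the infant has no illness, or only a minor one without fever, 4.6 does not stop the dose and, for minor illness, expressly permits it.
3. **Section 5.1.11, 7-day rule.** This ends study vaccination if a deferred dose cannot be given in time. It helps only an infant whose dose was deferred in the first place, so it adds nothing for one who passed step 2.
4. **Section 4.7.** If immunodeficiency is suspected, or there has been anaphylaxis, no further dose is given. Failure to thrive is not listed as a ground in itself.
5. **Section 5.1.11, pre-dose check.** Elimination criteria are checked before the dose, but no consequence is stated. For another criterion in the same 4.5 list, injection in the wrong limb, this section says that blinded vaccination continues and the child is removed from the according-to-protocol safety cohort. So meeting a 4.5 criterion does not in general stop dosing.
6. **Section 4.5.** The only stated effect is possible loss of evaluability.
7. **Sections 5.1.7 and 9.2.2.** Stopping is allowed, but neither section requires it.

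An infant who passes steps 2 to 4 meets no rule that obliges anyone to withhold the dose. The blinded doses still to come are three if onset is before Visit 3, two if between Visits 3 and 6, and one if between Visits 6 and 8.

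One practical detail affects the remedy. Section 5.4 schedules body weight at Visits 2, 5 and 7 and a physical examination at Visits 3, 6 and 8. Table 21 puts 12 to 21 days between each of those weights and the blinded dose that follows. The information needed for a judgement before each dose is therefore already collected, though the weight is not from the same day.

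**The case against.** The strongest objection is that the purpose is found only in the amendment rationale, and that no two operative clauses conflict. Read alone, 4.5 is coherent: failure to thrive affects evaluability like its neighbours. A mismatch with an amendment log usually proves nothing, because a log describes text that has been replaced. Here, however, the sentence explains a bullet that is still in force, so it is fair evidence of what that bullet was meant to do.

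The second objection is that the gap is narrow, and this stands. Grading of illness under 4.6 is left to the clinician, and many infants who fail to thrive could be judged at least moderately ill. Each blinded-dose visit includes an examination and a check of contraindications, and a check made before a dose can naturally be read as bearing on that dose. The Local Safety Monitor acts as the volunteer's advocate and advises investigators. These safeguards make withholding likely in many cases. They do not make it mandatory, and the stated aim was to ensure it.

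A reader might infer more than the text supports:

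- That the protocol lets any infant who fails to thrive be dosed. It does not: 4.6, the 7-day rule and 4.7 stop those who also have a qualifying illness or condition.
- That 4.7 protects only one arm because it opens by naming RTS,S/AS02D. Its next sentence bars additional doses of vaccine without naming a product, and a blinded investigator has to apply it to both arms.
- That the safety results are compromised. The primary SAE analysis in 10.9.1.1 uses the Total Vaccinated Cohort, which keeps these infants.

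**Conclusion.** The point holds in a limited form. The placement of the criterion does not deliver its stated purpose: for an infant who fails to thrive and has none of the conditions in 4.6 or 4.7, withholding further blinded vaccine is discretionary when it was meant to be assured.

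The number of infants concerned cannot be estimated. The protocol gives no incidence of failure to thrive and no basis for the share already stopped by other rules, so any count would rest wholly on assumption. The primary analysis is not materially affected. The conclusion rests on taking the Appendix H rationale as the sponsor's intent for text still in force, and on reading 4.5 and 5.1.11 as written. The case for correcting it is participant protection and consistent handling in a first trial in infants, at negligible cost.

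**What to change.** By amendment, add failure to thrive to 4.7 as a contraindication to further blinded vaccine, worded for RTS,S/AS02D or Engerix-B so that the arms are handled alike. Let the investigator judge it at the examination before each blinded dose, using the weights already taken. Add a cross-reference from 4.5 to 4.7. State that safety follow-up continues and that licensed vaccines are completed under 5.1.7, to which 4.7 already points.

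A numeric trigger, such as the weight-for-age Z-score below -2 used at entry, is optional. It measures attained weight and would miss an infant who falters but stays above the cut, so it should not replace clinical judgement.

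The cost is one bullet and one cross-reference, with ethics committee approval of the amendment. No visit or measurement is added. The downside is that a few infants receive fewer blinded doses. Some of them may have only a temporary problem; a deferral under 4.6 would be the milder alternative, but the 7-day limit in 5.1.11 leaves little time for weight to recover.

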## 4.6. Contraindications to any vaccination dose

The following AEs constitute contraindications to administration of RTS,S/AS02D at that point in time; if any one of these AEs occurs at the time scheduled for vaccination, the subject may be vaccinated at a later date, within the time window specified in the protocol (see Section 5.3), or withdrawn at the discretion of the investigator (see Section 9). The subject must be followed until resolution of the event, as with any AE (see Section 8.6).

- Acute disease at the scheduled time of vaccination. Acute disease is defined as the presence of any moderate or severe illness, or a mild illness with axillary temperature ≥ 37.5°C (all vaccines can be administered to persons with a minor illness such as diarrhea, mild upper respiratory infection with or without low-grade febrile illness).
- Axillary temperature  $\geq$  37.5°C.
- A lesion that would prevent intramuscular injection in the left or right antero-lateral thighs

## 4.7. Contraindications to subsequent vaccination dose

The following adverse events (AEs) constitute absolute contraindications to further administration of RTS,S/AS02D. If any of these AEs occur during the study, the subject must not receive additional doses of vaccine but may continue other study procedures at the discretion of the investigator (see Section 9). The subject must be followed until resolution of the event, as with any AE (see Section 8.6):

- Anaphylactic reaction following the administration of vaccine(s).
- Any confirmed or suspected immunosuppressive or immunodeficient condition, including human immunodeficiency virus (HIV) infection.

See Section 5.1.7 for a description of how these children will receive further vaccinations with licensed vaccines.

# 5. CONDUCT OF STUDY

# 5.1. Ethics and regulatory considerations

The study will be conducted according to Good Clinical Practice (GCP), the appended Declaration of Helsinki (Protocol Appendix A), and local rules and regulations of the country.

The following two sections provide guidance to the study investigator of the minimal ethical and regulatory requirements required by GSK but the final responsibility for the interactions between the Institutional Review Boards (IRBs) and Independent Ethics

Committees (IECs) and for informed consent remain with the Principal Investigator and may be subject to local rules and regulations.

# 5.1.1. Institutional Review Board/Independent Ethics Committee (IRB/IEC)

The IRB/IEC must be constituted according to the local laws/customs of each participating country. The ICH Harmonized Tripartite Guideline for Good Clinical Practice recommends that the IRB/IEC should include:

(a) At least five members.

(b) At least one member whose primary area of interest is in a non-scientific area.

(c) At least one member who is independent of the institution/study site.

Only those IRB/IEC members who are independent of the investigator and the sponsor of the study should vote/provide opinion on a study-related matter.

A list of the professions of the IRB/IEC members should be obtained by the principal investigator

This protocol and any other documents that the IRB/IEC may need to fulfill its responsibilities, including subject recruitment procedures and information about payments and compensation available to subjects, will be submitted to the IRB/IEC by the principal investigator. Written unconditional approval of the IRB/IEC must be in the possession of the investigator and GSK Biologicals before commencement of the study. This approval must refer to the study by exact protocol title and number, and should identify the documents reviewed and state the date of review. Relevant GSK Biologicals' data will be supplied by the principal investigator to the independent IRB/IEC for review and approval of the protocol. Verification of IRB/IEC unconditional approval of the principal investigator to GSK Biologicals' Study Monitor, using the standard notification form, prior to shipment of vaccine supplies and CRFs to the site.

No deviations from, or changes to, the protocol should be initiated without prior written consent of the sponsor and IRB/IEC favorable opinion of an appropriate amendment except when necessary to eliminate immediate hazards to the subjects or when the change(s) involves only logistical or administrative aspects of the study (e.g., change of monitor[s], telephone number[s]). Modifications are submitted to the IRB/IEC for information only. However, written verification that the modification was submitted should be obtained. Approvals/verifications must be transmitted in writing to GSK Biologicals' Study Monitor by the principal investigator.

The IRB/IEC must be informed by GSK Biologicals' Study Monitor, of:

• all subsequent protocol amendments, informed consent changes or revisions of other documents originally submitted for review;

- serious and/or unexpected adverse events occurring during the study, where required,
- all subsequent protocol modifications (for information);
- new information that may affect adversely the safety of the subjects or the conduct of the study;
- an annual update and/or request for re-approval, where required;
- when the study has been completed, where required.

If a trial is prematurely terminated or suspended for reasons including, but not limited to, safety or ethical issues or severe non-compliance, the sponsor will promptly inform the regulatory authorities of the termination or suspension and the reason(s) for the termination or suspension. If required by applicable regulations, the investigator must inform the IEC/IRB promptly and provide the reason for the suspension or termination (see Section 5.1.3 and Appendix B for further details).

#### 5.1.2. Informed consent

The details of the informed consent process are provided in Appendix C. The following principles will also apply.

In obtaining and documenting informed consent, the investigator should comply with the applicable regulatory requirement(s), and should adhere to GCP and to the ethical principles that have their origin in the appended Declaration of Helsinki. Prior to the beginning of the trial, the investigator should have the IRB/IEC's written approval/favorable opinion of the written informed consent form and any other written information to be provided to the subjects' parents/guardians.

Information should be given in both oral and written form whenever possible and as deemed appropriate by the IRB/IEC.

An investigator or designate will describe the protocol to potential subjects' parents/guardians face to face. The Subject Information and Consent Form may be read to the subjects' parents/guardians, but, in any event, the investigator or designate shall give the subjects' parents/guardians ample opportunity to inquire about details of the study and ask any questions before dating and signing the Consent Form.

Subject information and consent forms must be in a language fully comprehensible to the prospective subjects' parents/guardians. Informed consent shall be documented by the use of a written consent form approved by the IRB/IEC and signed and dated by the subjects' parents/guardians and by the person who conducted the informed consent discussion. The signature confirms the consent is based on information that has been understood. All illiterate individuals will have the study, the Subject Information and Consent Form explained to them point by point by the interviewer in the presence of an impartial witness. The subjects' parents/guardians will thumbprint or sign the consent form. The witness will also sign and date the consent form. Oral witnessed consent will replace written consent only in countries where the local custom is contrary or if the subjects' parents'/guardians' incapacity precludes this and provided that the local legal obligations are fulfilled.

Each subject's signed informed consent form must be kept on file by the investigator for possible inspection by Regulatory Authorities and/or GSK Biologicals' professional and Regulatory Compliance persons. The subjects' parents/guardians should receive a copy of the signed and dated written informed consent form and any other written information provided to the subjects' parents/guardians and should receive copies of any signed and dated consent form updates. Any amendments to the written information will be provided to subjects' parents/guardians.

Both the informed consent discussion and the written informed consent form and any other written information to be provided to the subjects' parents/guardians should include explanations of the following:

(a) That the trial involves research.

(b) The purpose of the trial.

(c) The trial treatment(s) and the probability for random assignment to each treatment.

(d) The trial procedures to be followed, including all invasive procedures.

(e) The subject's parents'/guardians' responsibilities.

(f) Those aspects of the trial that are experimental.

(g) The reasonably foreseeable risks or inconveniences to the subjects and, when applicable, to an embryo, fetus or nursing infant.

(h) The reasonable expected benefits. When there is no intended clinical benefit to subjects, the subjects' parents/guardians should be made aware of this.

(i) The alternative procedure(s) or course(s) of treatment/methods of prevention that may be available to subjects, and their important potential benefits and risks.

(j) The compensation and/or treatment available to subjects in the event of trial-related injury.

(k) The anticipated prorated payment, if any, to subjects' parents/guardians for participating in the trial.

(1) The anticipated expenses, if any, to subjects' parents/guardians for participating in the trial.

(m) That the subjects' participation in the trial is voluntary and subjects' parents/guardians may refuse to participate or withdraw from the trial, at any time, without penalty or loss of benefits to which subjects are otherwise entitled.

(n) That the monitor(s), the auditor(s), the IRB/IEC, and the regulatory authority(ies) will be granted direct access to the subject's original medical records for verification of clinical trial procedures and/or data, without violating the confidentiality of subjects, to

the extent permitted by the applicable laws and regulations and that, by signing a written informed consent, the subject's parents/guardians is authorizing such access.

(o) That records identifying subjects will be kept confidential and, to the extent permitted by the applicable laws and/or regulations, will not be made publicly available. If the results of the trial are published, subjects' identity will remain confidential.

(p) That the subjects' parents/guardians will be informed in a timely manner if information becomes available that may be relevant to the subjects' parents/guardians willingness for continued participation in the trial.

(q) The person(s) to contact for further information regarding the trial and the rights of trial subjects, and who to contact in the event of trial-related injury.

(r) The foreseeable circumstances and/or reasons under which a subject's participation in the trial may be terminated.

(s) The expected duration of a subject's participation in the trial.

(t) The approximate number of subjects involved in the trial.

GSK Biologicals will prepare a model Informed Consent Form which will embody all the elements described above. While it is strongly recommended that this model document be followed as closely as possible, the informed consent requirements given in this document are not intended to pre-empt any local regulations which require additional information to be disclosed for informed consent to be legally effective. Clinical judgement, local regulations and requirements should guide the final structure and content of the document.

The investigator has the final responsibility for the final presentation of Informed Consent Form, respecting the mandatory requirements of local regulations. The consent form generated by the investigator with the assistance of the sponsor's representative, must be approved (along with the protocol, and any other necessary documentation) by the IRB/IEC and be acceptable to GSK Biologicals.

